6 STUDY INTERVENTION

6.1 STUDY INTERVENTION(S) ADMINISTRATION

6.1.1 STUDY INTERVENTION DESCRIPTION

All subjects will receive TMS treatment with intermittent theta burst stimulation (iTBS). The TMS devices are non-significant risk devices, in line with the criteria for exception from an IDE.

The TMS device to be used in this study is the MagVenture TMS Therapy[®] (MagPror30/Theta Burst option) with theta Burst stimulation (See User Guide). A B65-coil – FDA cleared figure 8 coil will be utilized for iTBS treatment. In 2018, MagVenture received FDA clearance for the 3 minute protocol which we market under the trademarked name Express TMS[®] for Major depressive disorder (Blumberger et al., 2018), but TMS is not approved by the FDA for symptoms in Alzheimer's disease.

Localite Neuro Navigator will utilized to stimulate brain regions identified by the Infinitome software and allows correct positioning of the patient and coil (https://www.magventure.com/tms-research/localite-neuronavigation).

6.1.2 DOSING AND ADMINISTRATION

There will be a total of 25 intermittent theta burst sessions (iTBS) spread evenly across 5 treatment visits (5 sessions per treatment visit), all distributed over a two-week period (#3 treatment visits during week 1 and #2 during week 2). Intermittent theta burst sessions will be administered at the following settings, which have been used in a standardized manner by our collaborators in their TMS clinic:

Table 3: TMS Treatment Parameters

Resting Motor Threshold	80%	
# of Pulses/Session	1200 pulses (40 cycles x 10 burst pulses x 3	
	pulses per burst pulse)	
Inter-Train Interval	8 sec	
Pulse Frequency in Burst	50 Hz	
Session Length	15-30 min	
Time between Sessions	45 min to Hour	
Number of Targets	3	
Number of Sessions per Day	5	
Treatment Days	5	
Total Pulses per Day	18,000	
Total Pulses for Treatment	90,000	

The treatment regime above will be applied to a total of three regions of interest or parcellations (right TGd + two other sites found to have greatest # of anomalies). The interval between treatment of separate regions of interest (target) will be 2 minutes. The interval between iTBS sessions within the same treatment visit will be 45-60 minutes. Details of the operations of TMS and intervention will be included in a SOP or User guide that will be kept on site.

During the treatment, the TMS operator will be in the room and trained to activate the seizure protocol

(https://healthpartnersconnect.sharepoint.com/:b:/r/sites/bhc/TMS%20Library/Safety/Emergency%20Management%2 0of%20Seizures%20Standing%20Order.pdf?csf=1&web=1&e=p5h4Gg. All patients will be screened with the TASS screening questions. Vital signs will be monitored prior to and after treatment in participants.

6.2 MEASURES TO MINIMIZE BIAS: RANDOMIZATION AND BLINDING

N/A

6.3 STUDY INTERVENTION COMPLIANCE

Each treatment will be recorded on CRFs developed internally and will be based on HealthPartners Behavioral Health Clinic workflow and documents.

6.4 CONCOMITANT THERAPY

Medications to be reported in the Case Report Form (CRF) are concomitant prescription medications, over-the-counter medications and supplements. Specifically, any medication with that increases the risk of seizure will be documented in CRF and judged by the PI if it is allowed in the study.

7 STUDY INTERVENTION DISCONTINUATION AND PARTICIPANT DISCONTINUATION/WITHDRAWAL

7.1 DISCONTINUATION OF STUDY INTERVENTION

If a clinically significant finding is identified (including, but not limited to changes from baseline) after enrollment, the investigator or qualified designee will determine if any change in participant management is needed. Any new clinically relevant finding will be reported as an adverse event (AE).

If the patient develops a seizure, the PI may discontinue the TMS treatment and early withdrawal procedures will be performed.

7.2 PARTICIPANT DISCONTINUATION/WITHDRAWAL FROM THE STUDY

Participants are free to withdraw from participation in the study at any time upon request.

An investigator may withdraw a participant from the study if:

- Any medical condition, event or situation occurs such that continued participation in the study would not be in the best interest of the subject.
- The participant meets an exclusion criterion (either newly developed or not previously recognized) that precludes further study participation.
- Significant study procedure non-compliance
- Lost-to-follow up; unable to contact subject

7.3 LOST TO FOLLOW-UP

The reason for participant discontinuation or withdrawal from the study will be recorded on the relevant CRFs. Subjects who sign the informed consent form and undergo only cognitive measures, and not imaging or TMS will not have completed participation and may be replaced.

A participant will be considered lost to follow-up if he or she fails to attend any scheduled study visit and study staff are unable to contact the participant after at least 5 attempts.

The following actions must be taken if a participant fails to attend any required study visit:

- Study staff will attempt to contact the participant, reschedule the missed visit, counsel the participant on the importance of maintaining the assigned visit schedule and ascertain if the participant wishes to and/or should continue in the study.
- Before a participant is deemed lost to follow-up, the investigator or designee will make every effort to regain contact with the participant (where possible, telephone calls or e-mail – if no answer leave a voicemail on the first and last attempt). These contact attempts will be documented.
- Should the participant continue to be unreachable, he or she will be considered to have withdrawn from the study with a primary reason of lost to follow-up.

8 STUDY ASSESSMENTS AND PROCEDURES

8.1 STUDY SCHEDULE

See Figure 1 under protocol summary.

8.1.1 SCREENING VISIT (VISIT 1) DAY 0

- This visit may be virtual or in-person at NSC
- This visit will last about 90 minutes
- Review, obtain and document consent from subject and caregiver (e-consent)
- Administer MMSE, CDR
- Review medical history, demographics to determine eligibility to participate
- Review history regarding any contraindications for MRI imaging
- Schedule study visits for individuals who are eligible and available for the duration of the study.

8.1.2 BASELINE VISIT (VISIT 2) -WEEK 1 (± 7 DAYS)

- Verify inclusion/exclusion criteria
- Neuropsychological battery as mentioned in Section 8.2.
- This visit is at the clinic (HealthPartners Neuroscience Center [NSC]), is about 2 hours. This may be extended depending on availability of Imaging slot.

- Subject will undergo MRI imaging as mentioned in section 8.2
- Subject will be screened for TMS safety
- Review concomitant medications
- Record any adverse or serious adverse events

8.1.3 TREATMENT VISIT (VISTS 3-5 AND VISITS 6,7) (5 DAYS OVER 2 WEEKS, ± 7 DAYS AFTER VISIT 2)

- Verify inclusion/exclusion criteria
- Motor threshold mapping in Visit 3. Visit 3 will be 5 -7 hours. Visits 4-7 will be 4-6 hours each.
- All visits will be at NSC
- Subject will receive 5 theta burst stimulation sessions at each of the treatment visits
- Visits will be on alternating days (weekdays)
- Review concomitant medications at each visit
- Record any adverse or serious adverse events at each visit

8.1.4 FOLLOW-UP/REPEAT VISIT (VISIT 8)(WEEK 10, 6 WEEKS AFTER VISIT 7 ± 7 DAYS)

- Verify inclusion/exclusion criteria
- Neuropsychological battery as mentioned in Section 8.2.
- This visit is at the clinic (HealthPartners Neuroscience Center [NSC]), is about 2 hours. This may be extended depending on availability of Imaging slot.
- Subject will undergo MRI imaging as mentioned in section 8.2
- Review concomitant medications
- Record any adverse or serious adverse events

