1.3 SCHEDULE OF ACTIVITIES (SOA)

Table 1: Study Visit Schedule

Procedure	Screening	Baseline	Treatment	Follow-up	Early Withdrawal
Visit #	Visit 1	Visit 2	Visits 3-7	Visit 8	
	Day 0	Week 1	Weeks 2-4	Week 10	
Window		\pm 7 Days	\pm 7 Days	\pm 7 Days	
Informed consent	Х				
Medical History	Х				
Demographics	Х				
MRI Contraindications	х	х	Х		
Concomitant Medications	Х	Х	х	x	x
Inclusion/Exclusion Criteria	х	Х	х		
MMSE	Х				
CDR	Х				
TMS Safety Questionnaire	Х	Х			
Physical Exam	Х				Х
RBANS		Х		Х	
GDS		Х		Х	
iTBS Treatment			Х		
MRI Imaging		Х		Х	
Adverse Events/Serious Adverse Events	Х	Х	Х	Х	x

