2.2 RISK/BENEFIT ASSESSMENT

2.2.1 KNOWN POTENTIAL RISKS

Transcranial Magnetic Stimulation (TMS)

The TMS device to be used in this study is the MagVenture TMS Therapy[®] with theta Burst stimulation. MagVenture is a computerized, electromechanical medical device that produces and delivers non-invasive, magnetic fields to induce electrical currents targeting specific regions of the brain. In 2018, MagVenture received FDA clearance for the 3 minute protocol which we market under the trademarked name Express TMS[®]. The Lancet: "THREE-D: a randomized non-inferiority trial"), comparing the standard, 37 minute TMS protocol to the newer, 3 minute Theta Burst protocol (TBS) (Blumberger et al., 2018). The study concluded that the Theta Burst protocol is just as safe and effective for the treatment of major depressive disorder as standard TMS. Recent safety review of TMS summarizes the Theta Burst studies and concludes that TBS in the range of 80-100% of motor threshold is safe (Supplementary Table 5, (Rossi et al., 2020)). In this study, the planned motor threshold is 80%.

The TMS devices are non-significant risk devices, in line with the criteria for exception from an IDE. Transcranial magnetic stimulation (TMS) is a therapeutic tool, consisting of magnet and coil that utilizes Faraday's principle to induce electric currents in specific brain regions, leading to cortical excitability or suppression (Janicak & Dokucu, 2015) . The treatment is relatively safe with the most common side effect being tension headache (to which patients frequently acclimate over time) and is FDA-approved for the treatment of depression (Janicak & Dokucu, 2015). The device is routinely used in outpatient psychiatry clinics including HealthPartners and Park Nicollet behavioral health. Patients are generally able to drive home or return to work immediately after an TMS session. Rare side effects include dizziness, memory trouble, trouble concentrating and sudden mood changes. The long-term effects of TMS are not known.

Magnetic Resonance Imaging (MRI)

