2.2.3 ASSESSMENT OF POTENTIAL RISKS AND BENEFITS

We believe the potential risks to the participants in this study are minimal.

The following measures will be taken to protect patients from risk of TMS

 Transcranial magnetic stimulation is associated with a 50% risk of self-limiting headache and a 1/10,000 risk of seizures. All patients will undergo the TMS Adult Safety Screen (TASS), which will ensure that the risk of seizure is negligible for each subject participating in the study. In the event of adverse events during TMS treatment, specific procedures will be outlined (aligned with HealthPartners Behavioral Health) and staff will be trained and on-site for any assistance. In addition, all research staff will be

trained on the operation of device (Fried et al., 2020). Repeated exposure to TMS may result in sensorineural hearing loss, which is prevented by routine use of ear plugs.

• Relative to most oral medications used in treatment of dementia, TMS has a very favorable side effect profile.

The following measures will be taken to protect providers and patients from the risk of breach of confidentiality:

- A unique study ID code unrelated to the medical record number or other study subjectspecific information will be assigned to each patient and used to link data from various sources and needed for analysis. The study number will be used on the RedCap database and Infinitome Program. All imaging data uploaded from the NSC research site will be deidentified and uploaded to the Infinitome cloud-based server.
- Infinitome program uses an industrial grade cyber security that is superior to what is
 offered at the leading medical device companies. No personal health information is
 stored on servers and only de-identified scans are stored on a dedicated edge node on
 encrypted MinIO instances. Patient data is only accessed through authenticated calls
 form Kubernetes pods contained in the VPC. The web service requires user
 authentication. Only the data related to a specific facility can be retrieved through
 authenticated calls and are restricted to their use.

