8.4.4 TIME PERIOD AND FREQUENCY FOR EVENT ASSESSMENT AND FOLLOW-UP

Upon consenting, a subject is considered to be a participant in the study, and until that person either withdraws or completes study, AEs and SAEs will be recorded. The investigational team will promptly report any AE/SAE as required per federal guidelines.

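### No adverse-event contact is scheduled between the last treatment visit and Visit 8, 35 to 49 days later, and the caregiver is not named as a source: an early call would be a cheap, optional improvement

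*Combined protocol and SAP*

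**What the plan says.** Section 6.1.2 gives 25 theta burst sessions, "spread evenly across 5 treatment visits (5 sessions per treatment visit"). Section 8.1.3 instructs staff to "Record any adverse or serious adverse events at each visit" during treatment, and the Table 1 row "Adverse Events/Serious Adverse Events" is marked for screening, baseline, Visits 3-7, Visit 8 and early withdrawal. Table 1 has no column between Visits 3-7 and Visit 8. Section 8.1.4 sets Visit 8 at "WEEK 10, 6 WEEKS AFTER VISIT 7 ± 7 DAYS".

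On what happens between visits, section 8.4.4 says that "until that person either withdraws or completes study, AEs and SAEs will be recorded". It gives the period, but not how often, by what means, or of whom staff should ask. Section 7.3 describes telephone and e-mail contact, but under the condition "The following actions must be taken if a participant fails to attend any required study visit".

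On expected effects, section 2.2.3 states "Transcranial magnetic stimulation is associated with a 50% risk of self-limiting headache", and section 2.2.1 states "Rare side effects include dizziness, memory trouble, trouble concentrating and sudden mood changes".

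The caregiver takes part in consent (8.1.1, 10.1.1), and an informant contributes to the CDR at screening (8.2.3). Sections 8.4.1 to 8.4.4 do not mention either as a source of adverse-event reports.

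**The concern.** The five treatment visits carry the same dose but do not get the same follow-up. After Visits 3 to 6 the next scheduled question about adverse events comes at the next treatment visit, within the two-week course. After Visit 7 it comes at Visit 8.

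The effects that the protocol lists include some that are short-lived (headache) and some that resemble the disease under study (memory, concentration, mood). A brief event on the evening of the last treatment day would have to be volunteered, or recalled weeks later by a person with cognitive impairment. Visit 8 repeats the RBANS and GDS, which could show a change that lasts until then but not one that has resolved. What is at stake is the completeness of the safety record of a 10-person pilot meant to support a larger study, for a use of TMS that section 6.1.1 says is not FDA-approved.

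**Working it through.** **Inputs.** Visit 8 is 6 weeks ± 7 days after Visit 7 (8.1.4). Table 1 places treatment in Weeks 2-4 and follow-up at Week 10. There are 5 sessions at each of 5 visits, 1,200 pulses per session per target, and 3 targets (6.1.2, Table 3). Participation lasts 10-12 weeks (1.1). There are 10 participants (section 5).

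**1. The interval.** 6 × 7 = 42 days; 42 − 7 = 35 and 42 + 7 = 49. Table 1 agrees: (10 − 4) × 7 = 42 days. If treatment ended in Week 3 and Visit 8 were timed from the Week 10 label alone, the interval would be (10 − 3) × 7 ± 7 = 42 to 56 days. Section 8.1.4 ties Visit 8 to Visit 7, so 35 to 49 days is the right reading.

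**2. Who waits that long.** An event that starts *d* days after Visit 7 is first asked about 35 − *d* to 49 − *d* days after onset (for *d* up to 35).

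- *d* = 0: 35 to 49 days.
- *d* = 30: 5 to 19 days.

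The full wait therefore applies only to onset on the day of Visit 7.

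**3. Dose given at Visit 7.** The plan's own totals reproduce: 1,200 × 3 × 5 = 18,000 pulses per day, and 18,000 × 5 = 90,000 in all. Visit 7 gives 5/25 = 18,000/90,000 = 20%.

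**4. Share of participation.** 42/84 = 50% (12 weeks) to 42/70 = 60% (10 weeks). This is calendar time off treatment, not a share of risk.

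**5. Effect of a call 2 to 7 days after Visit 7.** For an event on the day of Visit 7, the wait falls from 35-49 days to 2-7 days. The interval from call to Visit 8 is then 35 − 7 = 28 days at the shortest and 49 − 2 = 47 days at the longest. The call serves events soon after the last session; it hardly shortens the remaining interval.

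**6. What cannot be calculated.** The documents give no rate or timing of events after the end of treatment, so neither the number missed now nor the number recovered by a call can be derived.

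**The case against.** The strongest case on the other side is that little is likely to be lost.

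- Recording runs from consent to completion, so any volunteered event counts. Visit 8 asks about adverse events and reviews concomitant medication, which can reveal a treated event.
- Headache is described as self-limiting and as something patients often get used to, and four of the five treatment days have a prompt follow-up question. Visit 7 itself lasts 4-6 hours, with 45-60 minutes between sessions, an operator in the room during treatment, and vital signs taken afterwards. Much of what follows the first four sessions that day would begin under observation.
- The other listed effects are called rare, and there are only 10 participants.
- Eligibility requires MMSE above 24 and CDR 0.5-1, so failure of recall is an inference, not a measured quantity.
- Safety is not an objective or endpoint in section 3, and section 9 plans no adverse-event analysis.
- Section 8.1 refers to Figure 1, which could not be read. Nor could the consent pages or the text between 10.1.3 and 10.1.5. Any of these, or the site's operating procedures, may say whom to call and who is asked.

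All of this stands, and it sets the weight of the point. It does not remove the point: the sections that can be read schedule no question and name no informant for the period after the last treatment day.

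A reader might infer more than the documents support. They do not show that every event after Visit 7 waits 35 to 49 days (step 2), that 20% of the pulses means 20% of the events, or that recording stops after Visit 7. Nor do they show that reports to the safety officer are delayed.

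**Conclusion.** The gap is real in the text that can be read, and its consequence is modest. An unvolunteered event on the day of Visit 7 is first asked about 35 to 49 days later, and one with later onset sooner. The caregiver, already involved in consent, is not named as an adverse-event source.

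The primary analysis and the RBANS and GDS analyses do not use adverse-event data, so no planned estimate is biased. The point rests on two assumptions: that no contact is described in the parts that could not be read, and that people with MCI or mild AD may fail to recall or mention brief events over 5 to 7 weeks. The second is reasonable, but the documents do not quantify it. This is an optional, inexpensive improvement in safety ascertainment.

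**What to change.** In Table 1, 8.1.4 and 8.4.4:

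- Add one short scripted adverse-event telephone contact with participant and caregiver about 2 to 7 days after Visit 7, asking about anything since leaving that visit. This is similar to the spacing between treatment visits. A call at 2 to 3 weeks would suit brief events less well, because it would still depend on 14 to 21 days of recall.
- At Visit 8, also ask the caregiver, in person or by telephone, about adverse events since that call.

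If Figure 1 or the consent form already provides for such a contact, it is enough to enter it in Table 1 and 8.1.4 and to name the caregiver.

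Cost: 10 × 1 = 10 calls after Visit 7, plus up to 10 caregiver calls where the caregiver does not attend Visit 8, so about 10 to 20 brief calls by existing staff. There is also one more column in Table 1 and some caregiver time.

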8.2 EFFICACY ASSESSMENTS

8.2.1 DEMOGRAPHICS AND MEDICAL HISTORY

Demographic information will be collected, including: gender, age, race, ethnicity, height, weight, BMI, education, dementia diagnosis, co-morbidities (such as Diabetes, Hypertension) and e-mail address for consent.

8.2.2 MMSE (MINI-MENTAL STATUS EXAMINATION)

Originally developed in 1976 by Folstein, the MMSE is a paper-based test commonly used in clinical and research settings (Folstein, Folstein, & McHugh, 1975). A 30 point cognitive screening tool that assesses orientation, working memory, short term memory, visuospatial construction, and language. This will be used in the screening visit for eligibility of participants in the study

8.2.3 CLINICAL DEMENTIA RATING (CDR)

The CDR is a 5-point scale used to characterize six domains of cognitive and functional performance applicable to Alzheimer disease and related dementias: Memory, Orientation, Judgment & Problem Solving, Community Affairs, Home & Hobbies, and Personal Care *http://alzheimer.wustl.edu/cdr/aboutcdr.htm*. The necessary information to make each rating is obtained through a semi-structured interview of the patient and a reliable informant or collateral source (e.g., family member). The CDR table

(*http://knightadrc.wustl.edu/cdr/PDFs/CDR_Table.pdf*) provides descriptive anchors that guide the clinician in making appropriate ratings based on interview data and clinical judgment. In addition to ratings for each domain, an overall CDR score may be calculated through the use of an algorithm. This score is useful for characterizing and tracking a patient's level of impairment/dementia:

CDR-0.5 = very mild dementia

CDR-1 = mild

CDR-2 = moderate

CDR-3 = severe

In addition, the total CDR ratings for each of the six cognitive/functional domains can be added to create a CDR sum of boxes (SOB). This will be used in the screening visit for eligibility of participants in the study

8.2.4 NEUROPSYCHOLOGICAL ASSESSMENTS

All enrolled subjects will undergo the following cognitive scales. These will be administered by the research staff trained in these assessments using instructions specific for tests under the guidance/ supervision of the study neuropsychologist.

8.2.4.1 REPEATABLE BATTERY FOR THE ASSESSMENT OF NEUROPSYCHOLOGICAL STATE (RBANS)

The RBANS is a brief, individually administered neurocognitive battery measuring immediate and delayed memory, attention, language, and visuospatial skills. The RBANS is a "pencil-andpaper" test and requires only a stimulus booklet and record form for administration and scoring. It is specially designed for repeat evaluations and includes alternate forms to control for practice effects related to content. The measure is broadly used for clinical diagnostic purposes and has also been increasingly employed as an endpoint in clinical trial investigations of medications believed to impact neurocognitive status. The RBANS will be administered by a research staff member to early stage AD subjects at baseline and 6 weeks after treatment to assess for response to TBS intervention

8.2.5 MOOD ASSESSMENTS

8.2.5.1 GERIATRIC DEPRESSION SCALE (GDS)

The GDS is a screening measure for depression in older patients

(http://neurosciencecme.com/library/rating_scales/depression_geriatric_ long.pdf). The scale will be administered by research staff at baseline and 6 weeks after TBS treatment.

